4.4. Withdrawal criteria

If any of the following situations occur during this trial, the investigator must discontinue the trial and withdraw the subject. Before withdrawal, the investigator must complete the last evaluation of various markers. The reason and date of the subject's withdrawal will be recorded in detail, and a safety visit shall be performed within 30 days after withdrawal.

- (1) The subject withdraws informed consent and requests to withdraw from the trial;
- (2) Radiological examinations show tumor progression;

*If the subject's clinical disease is stable without significant progression, existing treatment can be continued after a discussion is held with the patient, and informed consent is obtained. Following this, a radiologic evaluation will be performed after 4–6 weeks for confirmation, and treatment can be discontinued if progression is reconfirmed.

- (3) Occurrence of serious adverse events;
- (4) Occurrence of intolerable toxicity;
- (5) Other complications that in the investigator's judgment, make it inappropriate for the subject to continue;
- (6) The subject has poor compliance and does not take the drug on time or at the prescribed dose or does not comply with the study procedures;
- (7) Simultaneous use of other antineoplastic drugs;
- (8) Death of the Subject;
- (9) Loss to follow-up.

5. Investigational Drug and Treatment Design

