6.1. Overall principles

Dose modification must be based on the most severe drug toxicity that occurred in the previous dosing cycle. Three days before each dosing of the investigational drug on Day 1, the blood, liver, and renal function test results of the subject must meet the dosing requirements. All other toxicities must be resolved to CTCAE v4.03 Grade 0–1 or baseline

level (except for alopecia, fatigue, special regulations in the protocol, or other conditions that are deemed not clinically significant by the investigator). If the subject is not dosed as scheduled due to drug toxicity, the next dose can be delayed. If an investigational drug needs to be suspended/permanently discontinued due to investigational drug-related toxicity or other reasons, other investigational drug(s) can be used independently if the corresponding criteria are met. All dose modifications must be recorded in the file, including the reason and management.

AEs related to sintilimab exposure may stem from immunological etiologies. These immune-related AEs (irAEs) may occur within a short period after the first dose or several months after the last dose of sintilimab. They may affect more than one system simultaneously. Based on existing clinical trial data, most irAEs are reversible and can be managed by drug dosing interruption, administration of glucocorticoids, and/or other supportive treatments. For suspected irAEs, an appropriate evaluation must be performed to confirm the etiology or rule out other causes. Other procedures or tests, such as bronchoscopy, endoscopy, or skin biopsy, can be included in this evaluation. Sintilimab will be suspended or permanently discontinued, and glucocorticoids will be administered based on irAE severity. For dose modification and toxicity management guidelines for potential irAE, please refer to the “Management manual for immune-related adverse event” provided by the pharmaceutical company.

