6.4 Dose modification for anlotinib

If the investigator confirms that toxicity is mainly caused by anlotinib, dose reduction for

anlotinib alone is acceptable. If toxicity caused by 2 or more drugs cannot be confirmed, dose reduction should be performed for all related drugs. If anlotinib dosing is delayed during treatment (3 weeks per cycle), all future dosing dates will be delayed to ensure that the dosing interval between anlotinib treatment cycles is 21 ± 3 days. The anlotinib cycles and sintilimab cycles will be synchronized as much as possible by adjustments of permissible time windows.

The adverse reactions caused by **anlotinib** can be managed with symptomatic treatment, drug discontinuation, and/or dose modification. It is recommended that the dose be adjusted under the physician's guidance according to the severity of the adverse reaction: ① First dose modification: 10 mg, qd; ② Second dose modification: 8 mg, qd. If a third dose modification is required, the drug should be permanently discontinued.

When on 8 mg doses, the dose can be increased to 10 mg if necessary, depending on the adverse reaction.

When a drug-related adverse reaction occurs, the general rules in Table 3 should be consulted for dose modifications. When adverse reactions such as abnormal liver function [including ALT elevation, AST elevation, or total bilirubin elevation], proteinuria, decreased platelet count, or a bleeding event occur, dose modification and management are performed according to the principles in Tables 4–7.

Table 3. General rules of anlotinib dose modification for various grades of adverse reactions

Adverse reaction grade	Dosing time	Dose modification principle
Grade 3	Drug interruption until adverse reaction resolves to grade <2	Subsequent doses are reduced by one level; If the patient does not recover after 2 weeks, consider permanent discontinuation of the drug.
Grade 4	Drug interruption until adverse reaction resolves to grade <2	Subsequent doses are reduced by one level. Consider permanent drug discontinuation if the patient does not recover after 2 weeks, or consider permanent drug discontinuation based on the physician's judgment.

Table 4. Dose modification principles and management recommendations in case of abnormal hepatic function

Adverse reaction grade	Dose modification principle	Management recommendations

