Grade 2 (normal baseline)	Drug interruption. If AE resolves to grade <2 within 2 weeks, continue the drug treatment at a dose reduced by one level	Aggressive hepatoprotective treatment should be performed, and hepatic function is monitored once every week
Grade 2 (Abnormal baseline)	Continue drug treatment at the original dose	
Grade 3	Drug interruption. If AE resolves to grade <2 within 2 weeks, continue drug treatment at a dose reduced by one level	Aggressive hepatoprotective treatment should be performed, and hepatic function is monitored once every 2 weeks until toxicity restores to Grade <2 or can be explained by other reasons
Grade 4	Permanent drug discontinuation	Aggressive hepatoprotective treatment should be performed, and hepatic function is monitored 1–2 times every week until toxicity resolves to Grade <2 or can be explained by other reasons

Table 4. Dose modification principles and management recommendations in case of proteinuria

Adverse reaction grade	Dose modification principle	Management recommendations
Grade 2, routine urine protein test ++, but 24 h urine protein quantitation test result of 1.0 g–2.0 g (not including).	Maintain original dose	Aggressive symptomatic treatment should be provided, and a routine urine test is performed once every week
Grade 2, routine urine protein test ++ or above, but 24 h urine protein quantitation test result of 2.0g–3.5 g (not including).	Drug interruption If AE resolves to grade <2 within 2 weeks, continue drug treatment at a dose reduced by one level.	Aggressive symptomatic treatment should be performed, and the drug permanently discontinued if the AE occurs for a 3rd time.
Grade 3: 24 h urine protein quantitation test result of ≥3.5 g	Drug interruption If AE resolves to grade <2 within 2 weeks, continue drug treatment at a dose reduced by one level.	Aggressive symptomatic treatment should be performed, and the drug permanently discontinued if the AE occurs for the 3rd time.

Table 6. Dose modification principles and management recommendations for decreased platelet count

Adverse reaction grade	Dose modification principle	Management recommendations
Grade 2, platelet count of 50–75 × 10 ⁹ /L	Drug interruption. If AE resolves to grade <2 within 1 week, continue drug treatment at the original dose	A routine blood test is performed once every 2–3 days; in the subsequent dosing period, a routine blood test is performed once a week

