Hepatotoxicity: In clinical studies, it was observed that oral administration of anlotinib could induce transient transaminase elevation or total bilirubin elevation. This product should be used with caution in patients with underlying serum transaminase and total bilirubin elevations. Studies have not been performed in patients with hepatic insufficiency; therefore, anlotinib should be used with caution. Close monitoring is required for patients with a medical history of hepatic insufficiency (hepatic function be tested once within the first 3 weeks of drug administration). This drug is prohibited in patients with severe hepatic insufficiency. Drug interruption is recommended if a Grade 3/4 transaminase and total bilirubin elevation occurs. At the same time, serum transaminase and total bilirubin should be monitored until their levels significantly decrease before resuming dosing. If a Grade 3/4 adverse reaction recurs after dosing is resumed, subsequent doses can be reduced by one level. Drug discontinuation is recommended if the adverse reaction persists.

Diarrhea: Product absorption may be affected if taken by patients with diarrhea. Therefore, diseases causing diarrhea should be actively treated. This product can be taken under the guidance of the physician after improvement. Drug interruption is recommended if Grade 3/4 diarrhea occurs when taking this product. If Grade 3/4 diarrhea recurs after dosing is resumed, subsequent doses can be reduced by one level. Drug discontinuation is recommended if the adverse reaction persists.

Wound healing complications: Studies of the effects of anlotinib on wound healing have yet to be conducted. In clinical studies, patients with unhealed wounds from major

surgeries within the past 4 weeks were excluded. Since there is limited evidence on when the patients can take anlotinib after surgery, it is recommended that this product be temporarily discontinued before surgery and for 30 days after surgery.

Effects on driving and machinery operation: Fatigue may occur during dosing. Patients should pay attention when driving or operating machinery.

7. Concomitant Treatment

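### After Grade 4 liver toxicity on anlotinib, the section 6.4 liver table stops the drug for good, while section 6.5 describes restarting it

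*Protocol*

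**What the plan says.** Protocol section 6.4 (Dose modification for anlotinib) singles out abnormal liver function, defined there to include raised ALT, AST or total bilirubin, and says that "dose modification and management are performed according to the principles in Tables 4–7". The table on abnormal hepatic function, the first of two numbered Table 4, gives at Grade 3: "Drug interruption. If AE resolves to grade <2 within 2 weeks, continue drug treatment at a dose reduced by one level". At Grade 4 it gives: "Permanent drug discontinuation". The Grade 4 row adds liver monitoring until recovery and offers no way back to dosing.

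Section 6.5 (Precautions for anlotinib), under Hepatotoxicity, covers the same drug and the same laboratory tests. It says "Drug interruption is recommended if a Grade 3/4 transaminase and total bilirubin elevation occurs". It then says that "serum transaminase and total bilirubin should be monitored until their levels significantly decrease before resuming dosing", and continues: "If a Grade 3/4 adverse reaction recurs after dosing is resumed, subsequent doses can be reduced by one level". Stopping the drug is recommended only if the reaction persists.

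**The concern.** The two sections prescribe different actions for the same event. After a Grade 4 liver elevation, the table ends anlotinib, whereas section 6.5 names Grade 4 and sets out how dosing restarts, with a further step for a recurrence after that restart.

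The stake is patient safety. Section 6.5 itself notes that anlotinib can raise transaminases or bilirubin, so the rule may well be needed. An investigator who follows section 6.5 could give more drug to a patient whom the table removes from it. Whether that restart counts as a protocol deviation would depend on which section is consulted.

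**Working it through.** No arithmetic applies, because the plan states no figure on this point. The check sets the two texts side by side and then asks whether any other text settles the difference.

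**Step 1. Compare the rules case by case.**

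| Event on anlotinib | 6.4 liver table | 6.5 Hepatotoxicity | Can both be followed? |
|---|---|---|---|
| Transaminase and bilirubin both Grade 4 | Stop for good | Interrupt, restart after values fall | No |
| Grade 4 elevation of one alone | Stop for good | Same as above if *and* is read as *or*; otherwise not covered | No under the *or* reading; otherwise only 6.4 speaks |
| Grade 4 on recurrence after a restart | Stop for good | One-level reduction possible; stop advised if it persists | No, with the same *and*/*or* limit |
| Grade 3 | Interrupt; restart one level lower if below Grade 2 within 2 weeks | Interrupt, restart after values fall; first restart dose and time limit not stated | Yes, the table supplies what 6.5 leaves out |

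The *and*/*or* question is open on the page. The Hepatotoxicity paragraph opens by speaking of transaminase *or* bilirubin elevation and uses *and* in the dosing sentence. The conflict is therefore certain for the combined elevation and conditional for an isolated one.

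**Step 2. Look for text that settles it.**

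- *General rules table in 6.4 (Table 3).* It allows a reduced dose after Grade 4, but section 6.4 directs liver toxicity to the specific table, so it does not reconcile the two.
- *Section 6.1.* Before each Day 1 dose, "the blood, liver, and renal function test results of the subject must meet the dosing requirements". No liver value is given there, and the sentence does not say whether a patient with a Grade 4 event may be dosed again.
- *Section 4.4.* The withdrawal criteria include "Occurrence of serious adverse events" and intolerable toxicity. The definition of a serious event in section 9.5.1 turns on outcomes such as hospital admission, disability, threat to life or death. A Grade 4 value that is only a laboratory finding need not meet it.
- *Bar on use in severe hepatic insufficiency (6.4 and 6.5).* This points toward stopping. However, the protocol does not equate a Grade 4 laboratory value with severe insufficiency, and the 6.5 paragraph that contains the bar also describes resumption after Grade 3/4.
- *Sintilimab rules in 6.2.* They stop sintilimab for Grade 3 or 4 liver toxicity related to that drug. Section 6.1 lets the other drug continue alone if its own criteria are met, so the anlotinib rule still decides anlotinib.

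None of these ranks section 6.4 against section 6.5 or resolves a laboratory-only Grade 4 event.

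**The case against.** The best defence is that section 6.4 already governs. Its direction to the tables is specific and worded as an instruction. Section 6.5 is headed as precautions, its liver text only recommends or permits, and parts of it read like product labelling; the skin-reaction paragraph even points to a dosage heading that this protocol does not have. On a specific-over-general reading, the table decides Grade 4. The bar on severe hepatic insufficiency pulls the same way, and a patient with both tests at Grade 4 is the one to whom it most likely applies.

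Much of this stands: stopping is the better-supported reading. It does not remove the problem, because the protocol never states that ranking. Nor is section 6.5 merely background. Its bleeding paragraph sets a firm permanent stop from Grade 3 upward, which agrees with the bleeding table in 6.4. A reader therefore has reason to treat section 6.5 as operative, and its liver paragraph names Grade 4 when it describes a restart.

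Two stronger readings are tempting, and the document supports neither. A reader might infer that Grade 3 liver events are contradictory too, but there section 6.5 is merely silent and both texts can be followed together. A reader might also extend the point to blood pressure, cardiac events and diarrhea, where section 6.5 mentions reduction on recurrence. Table 3 already gives a one-level reduction after Grade 3 or 4, and section 6.5 does not deny it.

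**Conclusion.** The contradiction holds for Grade 4 liver toxicity on anlotinib. It is certain when transaminase and bilirubin are both Grade 4. For an isolated Grade 4 elevation it rests on reading *and* in section 6.5 as *or*. Its size is no further anlotinib under the table, against a permitted restart under section 6.5 and a possible lower dose after a recurrence.

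The protocol gives no frequency for Grade 4 liver events and nothing on how often an investigator would restart, so no probability is put on it. A reader might infer that the trial's inference is compromised. It is not: the ORR endpoint, the sample size and the error rates do not depend on this rule. The point is a safety rule that is wrong as written and should be corrected.

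**What to change.** Amend the Hepatotoxicity paragraph of section 6.5 to match the 6.4 liver table:

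- **Grade 4** (ALT, AST or total bilirubin): discontinue anlotinib permanently.
- **Grade 3:** interrupt, and resume one level lower only if the event has resolved to below Grade 2 within 2 weeks.

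Cite the liver table by title, because two tables in section 6.4 carry the number 4.

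If a precedence sentence is added, it should say that the stricter rule applies wherever sections 6.4 and 6.5 differ. A sentence that simply lets the 6.4 tables prevail could weaken section 6.5 elsewhere: for several toxicities section 6.5 recommends stopping if the reaction persists, where Table 3 only asks the physician to consider it.

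The cost is a wording amendment to one paragraph and, optionally, one sentence, with no extra visits or patients. Some patients who might have restarted under section 6.5 would stop anlotinib or restart at a lower dose.

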7.1 Permitted concomitant therapies

Drugs that conform to the protocol requirements in the investigator's judgment (e.g., concomitant drugs used to treat disease-related symptoms and treatment-related AEs)

- Subjects who require long-term drug use for underlying diseases such as hypertension and diabetes can continue their previous drug treatment.
- Local surgery, minimally invasive treatment, or radiotherapy for isolated lesions (excluding the target lesion) during the study treatment period.
- Supportive treatment that alleviates tumor-related symptoms is permitted, such as bisphosphonate treatment for bone metastases.
- Topical glucocorticoid treatment is permitted, such as topical skin applications, eyedrops, nasal spray, inhalations, etc.
- Prophylactic use of colony-stimulating factors (G-CSF or GM-CSF) or erythropoietin is prohibited. Therapeutic use of colony-stimulating factors is permitted if febrile neutropenia and Grade 3–4 neutropenia occurs after the first course of treatment or if the investigator deems that conditions that threaten the patient's life may occur. Corresponding G-CSF or GM-CSF support can be administered in subsequent treatment courses depending on the patient's condition.
- Antihypertensive, antiemetic, antibiotic, analgesia, vitamins, oral dexamethasone, and blood products can be used as supportive treatment. Mouthwashes can be used for stomatitis treatment or prophylaxis.
- If hypothyroidism occurs during treatment, the investigator should provide treatment and monitoring based on the most feasible medical practices. An endocrinologist should be consulted, and management should be performed based on his/her recommendation. If hypothyroidism (Grade ≥ 1) occurs, thyroid hormone replacement therapy should be provided, and thyroid function tests should be performed more frequently. Subjects who receive thyroid hormone replacement therapy due to Grade 2 or 3 hypothyroidism should

continue treatment with the investigational drug at the initial dose. The investigational drug should be discontinued in subjects who develop Grade 4 hypothyroidism.

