14. Tumor evaluation includes irRECIST and RECIST 1.1. Radiologic tumor examinations usually include contrast-enhanced CT or MRI. The examination sites must include the chest, abdomen, and pelvic cavity. Enhanced cranial MRI scan must be performed at baseline for patients with suspected signs or symptoms of central nervous system metastases. The type of radiologic examinations received by a subject during the study period should be the same. Baseline evaluation will be performed within 28 days before the first dose. Radiologic tumor evaluation will be performed once in Week 2 (± 7 days) and Week 4 (± 7 days) after the start of dosing. Subsequently, radiologic tumor evaluation will be performed once every 3 treatment cycles (± 7 days) until the 10th cycle. After the 10th cycle, radiologic tumor evaluation will be performed once every 4 treatment cycles (± 7 days). After the investigator has evaluated the first radiologic progression based on irRECIST, current treatment can be continued if the patient has stable clinical disease without significant progression, and radiologic evaluation will be performed after 4–6 weeks for confirmation (based on irRECIST). If progression is not confirmed, study treatment can be continued.

1. Study Background and Theoretical Basis

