7.2. Prohibited concomitant therapies

The following treatments are prohibited during the study treatment period, and the subject must be asked whether he/she has received any new drug at each visit.

- Systemic chemotherapy or biologic therapy other than the study drug that has antineoplastic effects (except for cytokines used to treat adverse events caused by chemotherapy) and Chinese patent medicine with antineoplastic effects.
- Drugs with immunoregulatory effects, including but not limited to non-specific immunoregulators (e.g., thymosin, interferon, interleukin, immunoglobulin, gamma globulin), and Chinese patent medicines with immunoregulatory effects.
- Chemotherapeutic agents that are not stipulated in this protocol.
- Investigational drugs other than sintilimab.
- Radiotherapy used to control tumors (palliative radiotherapy is permitted as long as it is not used for the target lesion, such as radiotherapy for alleviating pain from bone metastases and symptoms of brain metastases).
- Live vaccines during the study. Injections of inactivated influenza vaccine for seasonal influenza are permitted, but live attenuated influenza vaccines for intranasal use are prohibited.
- Corticosteroids. Inhalational steroids are permitted for patients with asthma or chronic obstructive pulmonary disease. Corticosteroids are permitted for temporary use to alleviate dyspnea. Corticosteroids are permitted for the treatment of immune-related AEs. Note: Prophylactic use of corticosteroids to prevent anaphylaxis (e.g., pretreatment before intravenous administration of contrast agent or chemotherapy drug) is permitted.
- Prohibited drugs mentioned in the exclusion criteria.

8. Schedule of Events

This trial comprises three stages (screening period, treatment period, and end of treatment) after each patient signs the informed consent form.

8.1. In the screening period (Day-28 to Day-1), the following study procedures must be completed to ensure that the subject is eligible for this study:

- The informed consent form has been signed;

- Review of inclusion and exclusion criteria;
- Medical history including but not limited to demographic data, past medical history, past treatment history for endometrial cancer, and past and concomitant medications.
- Physical examination: height, weight, body surface area, vital signs (heart rate, blood pressure), comorbidities, and other discomforts;
- ECOG scoring;
- Electrocardiography (within 3 days before the 1st dose)

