During the screening, the first tumor radiologic examination must be performed within 28 days before treatment. Evaluation is performed once after the 2nd treatment cycle (C3) and once after the 4th treatment cycle (C5). Subsequently, an evaluation will be performed once after the 7th cycle (C8) and once after the 10th cycle (C11). After the 10th cycle, an evaluation will be performed once every 4 treatment cycles, and the time window for radiologic evaluation is ± 7 days. Additional examinations can be performed if clinical progression occurs. The investigator will simultaneously evaluate RECIST1.1 and record the results, but this will not be used as a reference for treatment. After the investigator has completed the first radiologic evaluation of disease progression based on irRECIST, current treatment can be continued if the patient has stable clinical disease; radiologic evaluation will be performed after 4–6 weeks for confirmation (based on irRECIST). Treatment will be discontinued if progression is confirmed. If progression is not confirmed, study treatment can be continued until PD is confirmed by radiologic evaluation. An unscheduled radiologic evaluation can be performed at any time if the patient suffers unstable clinical disease during the study.

The definition of unstable clinical disease is as follows:

- Development of clinically significant signs and symptoms suggesting disease progression (including worsening laboratory test values)
- Decrease in ECOG PS score

- Rapid disease progression
- Tumor progression at important anatomical sites that requires other emergency medical interventions (such as spinal cord compression)

Patients who require treatment discontinuation for reasons other than disease progression shown in the radiologic evaluation should undergo radiologic evaluation at the end of treatment and after that at scheduled time points stipulated in the protocol until any one of the following events occurs: start of new antineoplastic therapy, objective disease progression, withdrawal of informed consent by the subject, loss to follow-up, or death.

Baseline cranial CT/MRI examination should be performed before starting study treatment in subjects with known or suspected brain metastases at screening. During the study period, cranial CT/MRI evaluation should be performed on these subjects, and brain metastases are considered non-target lesions for evaluation.

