If the investigator cannot determine whether disease progression has occurred, particularly for non-target lesions and new lesions, the subject can continue treatment until clinical symptoms occur or the next scheduled evaluation where radiologic evaluation is repeated. If disease progression is confirmed, then the date of progression should be the initial date of discovery. For subjects who discontinue treatment due to treatment completion or reasons other than objective disease progression, radiologic tumor evaluation should be performed once at treatment completion/discontinuation. A subsequent radiologic evaluation should be performed according to a protocol-stipulated radiologic examination schedule until one of the following situations occurs: start of new antineoplastic therapy, objective disease progression, death, or end of the study, whichever comes first.

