9.5. Overall response determination

Overall evaluation of disease response involves all parameters listed in the following table. The best overall response refers to the best response recorded from the start of treatment to disease progression/recurrence (the lowest measurement recorded since the start of treatment is used as a reference for determining tumor worsening). The best response of the patient is determined by the measurement method and confirmation criteria.

Table 8. Timepoint efficacy determination based on irRECIST criteria.

Overall efficacy evaluation:

Target lesion	Non-target lesion	New lesion	Overall response
CR	CR	None	CR
CR	Non-CR/SD	None	PR
PR	PD absent	None	PR
SD	PD absent	None	SD
PD*	Any response	Present or absent	PD
Any response	PD	Present or absent	PD
Any response	Any response	Present	PD

*Reconfirmation according to irRECIST criteria is required

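### Sections 7.1 and 7.2 conflict on non-palliative radiotherapy to non-target lesions, and a progression treated locally before its irRECIST confirmation scan can drop out of PFS and DoR

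*Protocol*

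**What the plan says.** **Local treatment.** Section 7.1 of the protocol lists as permitted "Local surgery, minimally invasive treatment, or radiotherapy for isolated lesions (excluding the target lesion) during the study treatment period". It states no intent. Section 7.2 lists as prohibited "Radiotherapy used to control tumors (palliative radiotherapy is permitted as long as it is not used for the target lesion", and gives pain from bone metastases and symptoms of brain metastases as examples of the exception. Section 7.2 does not mention surgery or minimally invasive treatment.

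**Progression.** After a first irRECIST progression in a clinically stable patient, section 9.1 says "radiologic evaluation will be performed after 4–6 weeks for confirmation (based on irRECIST). Treatment will be discontinued if progression is confirmed", and then "If progression is not confirmed, study treatment can be continued until PD is confirmed by radiologic evaluation". Footnote 14 to Table 1 agrees: "If progression is not confirmed, study treatment can be continued". On dating, in the paragraph about uncertain progression (non-target and new lesions in particular), section 9.1 says "If disease progression is confirmed, then the date of progression should be the initial date of discovery". RECIST 1.1 runs alongside: "The investigator will simultaneously evaluate RECIST1.1 and record the results, but this will not be used as a reference for treatment".

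**Scoring.** In Table 8 (overall response determination), non-target PD or any new lesion makes the overall response PD whatever the target lesions do. The table's footnote, "Reconfirmation according to irRECIST criteria is required", is attached only to the target-lesion PD row.

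**Endpoints.** Section 2.2 sets PFS and DoR on both criteria. The definitions in section 9.4 name no criterion for PFS or DoR, and use both for ORR.

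**The concern.** Two things are at stake.

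The first is protocol conformity. The per-protocol set in section 11.1 requires that the patient kept to the protocol, and section 4.3 removes patients with serious violations. If 7.1 and 7.2 give opposite answers for the same radiotherapy, membership of an efficacy set depends on which section is read, and that choice could be made after the outcome is known.

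The second is attribution. Sparing the target lesion does not by itself protect the endpoint, because overall PD can come from the lesions that 7.1 allows to be treated. If such a lesion is removed or irradiated between the first progression scan and the confirmation scan, the second scan may not confirm. The progression is then neither counted nor dated, and the effect of local treatment is credited to the study drugs. For PFS and DoR, that error runs only in the favourable direction.

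**Working it through.** **1. The two sections side by side (non-target lesion)**

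| Treatment | Section 7.1 | Section 7.2 |
|---|---|---|
| Palliative radiotherapy | permitted if the lesion is isolated | permitted |
| Non-palliative radiotherapy, isolated lesion | permitted | prohibited |
| Surgery or minimally invasive treatment, isolated lesion | permitted | not addressed |

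Only the second row is a contradiction.

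**2. The route to an uncounted progression.** (a) A new lesion, or non-target PD, gives overall PD (Table 8). (b) The patient is clinically stable and continues, with a rescan at 4–6 weeks (section 9.1, Table 1 footnote 14). (c) The lesion is treated locally in that interval; 7.1 permits this. (d) The rescan does not confirm, and treatment continues. (e) The rule that returns the progression date to first discovery applies only on confirmation. PFS and DoR by irRECIST then run on to a later event or to censoring.

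Step (b) is itself contested. Table 8 asks for reconfirmation of target-lesion PD only, whereas section 9.1 and footnote 14 apply confirmation to a first progression in general, and section 9.1 also allows repeat evaluation of uncertain non-target and new lesions.

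**3. When ORR is touched.** Section 9.3 requires a target-lesion reduction of at least 30%, with no new lesion, held for 4 weeks. Best overall response is the best recorded up to progression. A patient who progresses after a maintained response is a responder in any case. ORR changes only if the treated progression comes before the target response or inside its 4-week maintenance.

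**4. The design, reproduced.** Inputs from section 3.1: null ORR 0.13, alternative 0.39, 7 patients in stage 1 (stop at 1 or fewer responses), 16 in stage 2, fail at 5 or fewer of 23.

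P(success | p) = Σ over x = 2 to 7 of P(X1 = x) × P(X2 ≥ 6 − x), with X1 ~ Bin(7, p) and X2 ~ Bin(16, p).

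At p = 0.13:
- x = 2: 0.1769 × 0.1448 = 0.0256
- x = 3: 0.0441 × 0.3461 = 0.0152
- x = 4: 0.00658 × 0.6347 = 0.0042
- x ≥ 5: 0.0006
- Sum: **0.0456**

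At p = 0.39 the same formula gives **0.800**. Both meet the stated 0.05 and 0.8, so no protocol figure is wrong.

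**5. Illustration: one false responder.** One patient is 1/23 = 4.3 percentage points of ORR. Suppose exactly one non-responder is counted as a responder.

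- Stage 1 unaffected: 5 true responses now suffice. At p = 0.13: 0.1769 × 0.3461 + 0.0441 × 0.6347 + 0.00658 × 0.8923 + 0.0006 = 0.0612 + 0.0280 + 0.0059 + 0.0006 = **0.096**.
- That patient is in stage 1: one true response now also passes stage 1. This adds the x = 1 term, 0.3946 × 0.1448 = 0.0572, giving **0.153**.

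Both figures are conditional on such a patient occurring. The protocol gives nothing from which to estimate how often that would be.

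**The case against.** The strongest reply has five parts.

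- **Section 7.2 can be read as the specific limit on the general permission in 7.1.** That is a possible reading, but the text does not say so. Two investigators could classify the same patient differently.
- **RECIST 1.1 is recorded in parallel, and section 11.2 gives exact intervals for ORR and DCR under both criteria.** This stands. The confirmation step is tied to irRECIST, so a first PD by RECIST 1.1 is not erased by this route. It does not close the point, because irRECIST results are also reported and section 9.4 does not say which criterion decides ORR, PFS or DoR.
- **Table 8 does not require reconfirmation of non-target or new-lesion PD.** True of the table, but footnote 14 and section 9.1 are broader. This is a further inconsistency rather than a safeguard.
- **The window is narrow.** Continuing requires stable clinical disease, expected major surgery is an exclusion, and section 6.5 recommends interrupting anlotinib around surgery. These limit how often surgery would occur, but none of them bars radiotherapy or minimally invasive treatment.
- **Scoring of local therapy is usually left to the SAP, which is not shown.** This also stands in part: the mere absence of a scoring rule is not an error in the protocol. What remains is what the protocol does state, namely conflicting conduct rules, conflicting confirmation rules, and a date that is restored only on confirmation.

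A reader might infer that 7.1 and 7.2 also conflict on surgery, or that local treatment generally inflates the number of responders. The documents support neither: 7.2 is silent on surgery, and target lesions, which drive response, may not be treated under 7.1.

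**Conclusion.** The point holds within limits. Sections 7.1 and 7.2 contradict each other on non-palliative radiotherapy to an isolated non-target lesion, with consequences for protocol conformity and the per-protocol set. Independently, the irRECIST confirmation and dating rules allow a locally treated non-target or new-lesion progression to go uncounted, so PFS and DoR by irRECIST can be too long. The effect on ORR is confined to the sequence in step 3 of the working.

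The size is illustrative. The rise from 0.046 to 0.096 or 0.153 assumes exactly one false responder; 0.096 is not a ceiling, because it assumes that stage 1 is untouched. Converting this into a general shift in ORR, such as an apparent 17% under a true 13% (null success probability 0.126), would need a rate of local treatment that the protocol does not give. The sample size and decision rule are not in question.

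**What to change.** 1. Reconcile sections 7.1 and 7.2 into one statement on radiotherapy to non-target lesions. Which clinical rule is right is not judged here.
2. Reconcile the Table 8 footnote with section 9.1 and Table 1 footnote 14 on which kinds of PD need confirmation.
3. State in the endpoint text that if a lesion that already met PD criteria (non-target PD or a new lesion) is treated locally before the confirmation scan, the progression stands. For PFS and DoR it is dated to the scan that first showed it, and a response first documented after that scan does not count in ORR.
4. State that a locally treated non-target lesion stays in the assessment as non-CR.
5. State that local treatment of a lesion that did not meet PD criteria is not by itself progression. Without this limit, palliative radiotherapy that both sections allow could be counted as an event and shorten PFS artificially.
6. Add one CRF flag for local therapy, with lesion and date.

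The cost is protocol wording and one data field. PFS, DoR or ORR may come out slightly less favourable. The sample size does not change.
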